two cervical epidural steroid injections would be very appropriate in the treatment of a specific episode of cervical radicular pain. This literature also suggests that a maximum of four injections can be used within six months, assuming there was a positive response and improvement seen with the previous injections.

Study Design

This is a randomized, double-blinded clinical trial. The total enrollment goal is 60 patients (30 per treatment group)

Objective

The purpose of this study is to determine the effectiveness of cervical transforaminal epidural steroid injections in decreasing the need for an operation in patients with cervical radicular pain, otherwise considered to be operative candidates.

Treatment Groups:

Patients will be randomized in a 1:1 fashion to one of the following treatment arms:

1. Cervical transforaminal injection: 1.0 cc Lidocaine 1.0% with 1.0 cc normal saline
2. Cervical transforaminal injection: 1.0 cc Lidocaine 1.0% with 1.0 cc of Dexamethasone (10 mg/cc)

Primary/Secondary Outcome Variables

Primary Outcome Variables: The primary outcome variable is the avoidance of surgery. Treatment success is defined as the avoidance of surgery, while treatment failure is defined as having surgery due to failure of the injection treatment to alleviate pain and improve function over the 12 months they are being followed for purposes of this study.

Secondary Outcome Variables: Secondary outcome variables include:

- Decreased disability as measured by the validated outcome measure tool, the Neck Disability Index (NDI).
- Decreased neck pain and radicular pain as measured by a numerical pain rating, Verbal Numeric Pain Score with 0 being no pain and 10 being the worst pain imaginable
- Patient Satisfaction as measured by a numerical pain rating, Verbal Numeric Pain Score with 0 being completely unsatisfied and 100 completely satisfied

Patient Selection and Treatment Plan

Patients deemed to be surgical candidates for the treatment of cervical radicular pain at OrthoCarolina, PA will be screened for eligibility and asked to participate in the study. Potential subjects will meet with a research coordinator to discuss the details of the study. Those who choose to participate will be consented accordingly.

Inclusion Criteria:

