1. Subjects who have cervical radicular pain without significant neurologic deficit (neurologic deficit is defined as manual muscle testing less than 3/5), MRI/CT findings of neural compression (neural compression is defined as disc herniation or central or foraminal spinal stenosis),
2. Failed 6 weeks of conservative treatment (conservative treatment is defined as relative rest, home exercise, physical therapy, and use of anti-inflammatory and/or analgesic medications),
3. Deemed to be good operative candidates by spine surgeons (patients with MRI/CT findings of neural compression with concordant symptoms) and had agreed to possible operative intervention

Exclusion Criteria:

1. History of
 - a. acute trauma,
 - b. diabetic neuropathy,
 - c. active infection,
2. Active progressive neurological deficit (neurologic is deficit defined as manual muscle testing less than 3/5),
3. Medical condition that may affect the cervical spine neurological exam and/or pain assessment (e.g. peripheral neuropathy),
4. More than one cervical level requiring injection,
5. Previous cervical fusion surgery,
6. Bleeding disorders or other medical contraindications to the injection procedure,
7. Absence of substantial radicular pain (radicular pain is defined as arm pain greater than neck pain),
8. Involvement in workers' compensation claim, or any litigation related to neck injury.
9. Patients who are pregnant, or who plan to become pregnant in the next 12 months

Data Collection and Treatment Administration

Data Collection

Screening Visit

The primary operator or blinded investigator and/or designee will screen patients for potential participation in the study. The following data points will be collected for all patients:

- Informed Consent
- Patient demographics (medical record number, age, gender, ethnicity, body mass index (BMI),

- Patient medical history (smoking history, acute trauma, diabetes (type I or type II), active infection, active progressive neurological deficit, bilateral disease, bleeding disorders or other medical contraindications to the injection procedure, presence of radicular pain)
- NDI questionnaire (disease specific measure), Verbal Numeric Pain Score, Pain Medication Use, and Neurological Exam

Blinding

This is a double-blind study (i.e., the patient and the blinded investigator are both unaware of the specific study treatment being administered).

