This protocol requires two types of investigators: **primary operators** and **blinded investigators**. The principal investigator and co-investigator(s) will determine who serves as primary operator and blinded investigator for each site. The site must clearly designate these roles prior to initiation of the study.

The **primary operator** will perform the primary study procedure. The primary operator is not blind to study treatment as he/she has to deliver the assigned therapy.

The **blinded investigator** will be blinded to study treatment and will perform all follow-up medical evaluations.

Methods used to preserve blinding are described in the relevant sections below.

Randomization

After obtaining informed consent, patients will be randomized by independent party to one of the two treatment groups. Patients will be randomized to either receive Cervical transforaminal injections with 1.0 cc of preservative-free lidocaine 1.0% and 1.0 cc of normal saline, or to receive Cervical transforaminal injections with 1.0cc of preservative-free Lidocaine and Dexamethasone (10mg/cc). A 1:1 randomization schedule will be followed. A random number generator will be used to determine the randomization schedule.

Within the operating room, staff will open the **sealed Randomization Envelope** (which has been prepared for the site in sequential order). Envelopes will be opened in the order for which patients are treated. The staff will notify the primary operator as necessary. **Do NOT call out the randomization; show the primary operator the randomization sheet within the envelope.** The randomization sheet will be filed in the patient's surgery center records and the primary operator will be instructed to dictate that the patient had a study injection and will not disclose the randomization.

Treatment Administration

Subjects will be scheduled to receive up to four cervical transforaminal injections after randomization. The injections will be scheduled at least 14 days apart and they will

receive no more than four injections within the 12 month period per the North American Spine Society (NASS) Review and Recommendation Statement.

The study procedure is performed by the primary operator. The blinded investigator must not be present.

Standardized procedure to be performed by OrthoCarolina physiatrists, using a technique similar to the following:

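### A primary operator who knows the allocation of the patients he or she has treated may screen new candidates; if the unstated schedule is restricted, later envelopes are partly predictable to that operator.

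*Combined protocol and SAP*

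**What the plan says.** Screening Visit, under Data Collection, lets any of three parties screen: "The primary operator or blinded investigator and/or designee will screen patients for potential participation in the study". The Blinding section says of one of them: "The primary operator is not blind to study treatment as he/she has to deliver the assigned therapy". Randomization explains how the operator learns the arm. Operating-room staff open the next sealed envelope and are told to "show the primary operator the randomization sheet within the envelope". Envelopes are used in the order in which patients are treated.

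On the sequence, the protocol says "A 1:1 randomization schedule will be followed" and that a random number generator produces it. It does not say whether the list is simple or restricted, or whether any block size is kept from operators. Study Design gives an enrolment goal of 60, 30 per group.

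The blinded investigator "will be blinded to study treatment and will perform all follow-up medical evaluations". Treatment Administration bars the operator from further patient contact after the procedure, except in a medical emergency. No section sets a matching limit before entry.

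**The concern.** Sealed envelopes hide the next sheet but not the earlier ones. On a restricted list, someone who remembers which arm has been used more often can guess the next envelope better than chance. If that person also decides who is eligible, prognosis at entry can become linked to the arm.

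There is room for this. Some exclusion criteria call for judgement: a condition that might disturb the examination or pain rating, the number of levels needing injection, and contraindications to the procedure. The primary outcome is avoidance of surgery, which patients may choose at any time, so it plausibly depends on how they were at entry. Blinding after entry cannot undo selection made before it.

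**Working it through.** **Inputs.** From the protocol: 60 patients, 30 per group (Study Design); 1:1 allocation (Randomization); 30% versus 70% avoiding surgery (Sample Size), so the planned difference is 70 − 30 = 40 points. The protocol gives no figure for predictability, so there is none to reproduce. Assumed, because not stated: the schedule type, the number of operators, the number of patients waiting, and the effect of steering, d = 10 points.

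**Step 1: guess rate with one operator and no queue.** The operator guesses the arm that is behind and tosses a coin when the arms are level. In a balanced block of size 2m, the expected number of correct guesses is m + (4^m / C(2m, m) − 1)/2.

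- Blocks of 4 (m = 2): 2 + (16/6 − 1)/2 = 2.833 per block; × 15 blocks = 42.5.
- Blocks of 6 (m = 3): 3 + (64/20 − 1)/2 = 4.1 per block; × 10 blocks = 41.0.
- One 30/30 list (m = 30): 30 + (9.749 − 1)/2 = 34.4.
- Simple randomization: 60 × 0.5 = 30.0.

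**Step 2: bias.** Suppose the enrolled patient's chance of avoiding surgery is d higher when the steroid arm is guessed, d lower when the control arm is guessed, and unchanged when the arms are level. With C correct guesses out of 60, the false difference is d × (2C − 60)/30, or 2d(2q − 1) with q = C/60.

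| Schedule | C of 60 | q | Bias at d = 10 points |
|---|---|---|---|
| Simple | 30.0 | 50% | 0 |
| One 30/30 list | 34.4 | 57% | 2.9 |
| Blocks of 6 | 41.0 | 68% | 7.3 |
| Blocks of 4 | 42.5 | 71% | 8.3 |

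**Step 3: several operators, blocks of 4.** Patients are shared at random among operators who exchange nothing (simulation, 3,000 runs). Two operators: q = 59.9%, bias 20 × (2 × 0.599 − 1) = 4.0 points. Three operators: q = 56.8%, bias 2.7 points.

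**Step 4: patients waiting, blocks of 4, one operator.** A candidate's envelope is not the next one if others screened earlier are still untreated.

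- None waiting: the four positions in a block are guessed at 1/2, 2/3, 2/3 and 1; mean 70.8%.
- One waiting: 1/2, 1/2, 2/3, 2/3; mean 58.3%, bias 3.3 points.
- Two waiting: 1/2, 1/2, 1/2, 2/3; mean 54.2%, bias 1.7 points.
- Three waiting: 50%, bias 0.

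**Step 5: effect on the test.** This simulation (4,000 runs) assumes no treatment effect, 50% avoiding surgery in both arms, one operator, no queue and d = 10. The false difference and two-sided type I error were 8.6 points and 10.2% for blocks of 4, 6.9 points and 8.0% for blocks of 6, 2.7 points and 5.6% for one 30/30 list, and 1.3 points and 5.0% for simple randomization. The small difference under simple randomization comes from chance imbalance in final arm sizes. With d = 0 the rejection rates ran from 4.7% to 6.0%, so the last two schedules show no clear inflation. Bias is proportional to d: at d = 20, blocks of 4 gave about 17 points and a type I error of about 26%.

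**The case against.** A reader might infer that the operator knows every earlier allocation. The documents do not support that. They speak of operators in the plural ("Standardized procedure to be performed by OrthoCarolina physiatrists"), and each is shown the sheets of his or her own patients. The sheet is then filed, and the operator is told not to disclose it in dictation. Full knowledge needs a single operator or shared information. Repeat injections given by a different operator would spread some of it.

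A reader might also infer that the schedule is predictable. That is not shown either. A random number generator with a 1:1 ratio is compatible with simple randomization, under which past sheets predict nothing. An enrolment goal of 30 per group hints at restriction without proving it, and blocks are nowhere mentioned. The only restriction the text hints at, one 30/30 list, gives about 3 points under the assumed shift.

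Other safeguards stand. Candidates must be "Deemed to be good operative candidates by spine surgeons", and referring physicians are blinded. A research coordinator discusses the study with candidates, an independent party randomizes after consent, and the radicular-pain criterion has a working definition. These reduce the risk. They do not remove it, because none is said to replace the screener's decision on eligibility.

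It is also fair that the operator's knowledge may be needed on the level to inject and on contraindications, and that changing the screener alone would leave the operator able to influence treatment order. The fix has to meet both points. Nothing here suggests that anyone would steer enrolment deliberately.

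**Conclusion.** The point holds as a conditional one. The protocol permits an unblinded operator to screen, nothing separates the two roles before entry, and the sequence method is unstated, so the text cannot show that later envelopes are unpredictable.

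For the schedules examined, the bias runs from about 0 to about 8 points against the planned 40. The upper end needs small blocks, one operator who has seen every sheet, no queue and a 10-point shift in prognosis that is purely assumed. Several operators or a short queue bring blocks of 4 down to about 4 points or less. This could not by itself produce the planned difference, but it would matter more if the true effect were smaller. It is a cheap improvement, not a fatal flaw.

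**What to change.** In the Screening Visit section, delete the primary operator from the screening sentence, so that the blinded investigator or a blinded designee makes and signs the eligibility decision before the patient is scheduled. Add that the operator may give procedural input on the level to inject and on contraindications, but neither makes the final eligibility decision nor sets the order in which study patients are treated.

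In the Randomization section, state whether the schedule is simple or restricted. If blocks are used, vary their size at random and keep the sizes from operators.

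A screener without allocation knowledge guesses at 50% under any 1:1 scheme, and the sample size does not change. The cost is a few sentences. Blinded staff are already named as screeners, so extra staff should not be needed, although the protocol does not say how many there are. The small downside is that operators could not themselves enrol patients they see first.

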Study patients can elect to abandon the injection treatment and elect to undergo surgical treatment at any point during the course of the study. It is defined as treatment failure if a study patient elects to undergo surgical treatment. Patients who elect to undergo surgery will be discontinued from the study and no further effectiveness evaluations will be performed. Patients, referring physicians, and evaluating physician assistants are blinded to the treatment group. The treating physiatrist will not be blinded to the medications but will not be performing any clinical follow-up exams.

Follow-up Office Visits

Patients will be asked to return to the clinic 4 weeks, 12 weeks, 6 months, 12 months (following their first injection date) and the following data points will be collected for both groups:

- NDI questionnaire (disease specific measure), Verbal Numeric Pain Score, Blinding Assessment (patient and investigator), Pain Medication Use, Neurological Exam, and Subject satisfaction.

In the event that the patient receives their second, third, or fourth injection within 1 week prior to one of their follow-up office visits, the post injection phone call data will be collected at that visit. The study coordinator will tell the subject their baseline, pre-procedure Verbal Numeric Pain Rating and ask the subject to rate their current radicular pain intensity. Patients will also be asked to rate their overall satisfaction with their treatment and their current narcotic medication use.

The full schedule of assessments is shown in study flow chart below.

Study Flow Chart:

Study procedure	Screening	0 (day of procedure, injection #1)	Phone Call	Injection #2 (At least 14-21 days after #1)	4 weeks post injection	12 weeks post injection	6 months post injection	12 months post injection
Informed Consent	x							
Inclusion/Exclusion	x							
Verbal Numeric Pain Score**	x		x		x	x	x	x
NDI	x				x	x	x	x
Neuro Exam	x				x	x	x	x
Injection*		x		x				
Blinding Assessment - Patient					x	x	x	x
Blinding Assessment - Investigator					x	x	x	x
Pain Medication Use	x	x	x	x	x	x	x	x
Subject satisfaction			x		x	x	x	x
Adverse Events			x	x	x	x	x	x

* Patients may receive up to four injections within the 12 month period. Injections will be scheduled at least 14 days apart.

** Patients will be called one week after injection 1, 3 (as needed), and 4 (as needed)

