***If an injection occurs within 1 week prior to follow-up visits, patient will not be called. Verbal Numeric Pain Scale, Pain Medication Use, Subject Satisfaction and Adverse Events will be recorded during the follow-up visit.

Unblinding Procedures

Patients will not be unblinded to their study treatment. Unblinding of patients will only occur by the data manager and statisticians in the event of an SAE that is deemed possibly or probably related. Subjects that have been “blind-broken” must be discontinued from the study and no further effectiveness evaluations will be performed. However, the SAE will continue to be followed up until resolution.

Sample Size

Sample size calculations are based on the study by Riew et al. (2000). We estimate that 30% patients randomized to Lidocaine will avoid surgery compared to 70% of the patients randomized to Lidocaine with Dexamethasone. With a level of significance of 0.05 and power of 80%, 23 patients are needed in each group. To account for a 30% attrition rate, 30 patients are needed in each group. The total enrollment goal is 60 patients.

Risks

As with all medications, side effects may include an allergic reaction. Allergic reactions may range from minor reactions, such as itching or rash, to major, life-threatening reactions which can result in death.

Risks associated with cervical transforaminal injections include, but are not limited to:

Likely

- Spinal headache;

Less Likely

- Nerve irritation;
- Nerve injury;
- The risk of bleeding and/or infection into the spinal area;
- Reaction to medications;

Rare, but Serious

- Lung collapse;
- Seizures
- Paralysis
- Loss of vision
- Stroke
- Death.

Risks of general anesthesia or moderate sedation include, but are not limited to:

The most common side effects may include:

- Headache
- Adverse reaction to medications

Less common side effects of may include:

- Bleeding sufficient to cause anemia or require transfusion
- Hematoma (bleeding from the procedure)
- Pseudoaneurysm (injury to a blood vessel)
- Seroma (a collection of fluid under the skin)
- Blood vessel injury
- Pneumonia

Rarely, side effects may include:

- Hypotension (drop in blood pressure)
- Cardiopulmonary arrest (heart attack)
- Stroke
- Pulmonary embolism (a blood clot to your lungs)

- Death

Risks associated with contrast agents that are used in the procedure include, but are not limited to:

- Allergic reaction
- Anaphylaxis
- Death

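### Radicular pain at office visits may be rated with or without a reminder of the baseline score, depending on how recently the last injection was given

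*Combined protocol and SAP*

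**What the plan says.** Under Primary/Secondary Outcome Variables, one secondary outcome is "Decreased neck pain and radicular pain as measured by a numerical pain rating, Verbal Numeric Pain Score", on a 0-10 scale.

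Follow-up Office Visits sets visits at 4 weeks, 12 weeks, 6 months and 12 months after the first injection. The items collected at each are "NDI questionnaire (disease specific measure), Verbal Numeric Pain Score, Blinding Assessment (patient and investigator), Pain Medication Use, Neurological Exam, and Subject satisfaction". Nothing there says how the pain question is put.

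The same section then makes an exception. "In the event that the patient receives their second, third, or fourth injection within 1 week prior to one of their follow-up office visits", the call data are collected at the visit, and the instruction is: "The study coordinator will tell the subject their baseline, pre-procedure Verbal Numeric Pain Rating and ask the subject to rate" current radicular pain. A footnote to the Study Flow Chart agrees: "If an injection occurs within 1 week prior to follow-up visits, patient will not be called". It adds: "Verbal Numeric Pain Scale, Pain Medication Use, Subject Satisfaction and Adverse Events will be recorded during the follow-up visit".

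Who has a recent injection at a visit is governed by Follow-up Phone Calls to Patient/Additional Injections and the subsections after it. Two injections are booked for every patient at the start, at least 14 days apart. The second may be cancelled after a good response or after a poor one. The third and fourth are given if needed.

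The Statistical analysis section has no rule for flagging, separating or adjusting for ratings given after a reminder.

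**The concern.** Reminding a patient of the baseline score can change the answer to a question about current pain. If some scheduled scores follow a reminder and others do not, one outcome variable holds two kinds of measurement.

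Applying the same rule in both arms does not fully settle this. The trigger is a recent repeat injection, which happens after randomization and can depend on how well the assigned treatment worked. If the arms differ in repeat injections near visits, they differ in the share of prompted scores, and part of any difference in radicular pain could come from the questioning. Even with equal shares, mixing two methods can add noise in a trial of 30 patients per group.

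**Working it through.** The plan states no figure that depends on this point. Its only sample-size calculation concerns surgery avoidance. The check is therefore a reading of the text, a day count, and an illustration on stated assumptions.

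**1. Ordinary and triggered visits**

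| | Ordinary visit | Visit within 1 week after injection 2, 3 or 4 |
|---|---|---|
| Pain item | Listed | Listed, and call data also due |
| Reminder of baseline | None scripted | Scripted before the radicular pain rating |
| Neck pain | No reminder scripted | No reminder scripted |
| Separate phone call | As scheduled | None; score recorded at the visit |

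The text does not say whether a triggered visit yields one radicular score or two.

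**2. Timing at week 4**

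Put the visit at day 28. The trigger is 0 to 7 days since the injection, so the first triggering day is 28 - 7 = 21.

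- Injection 2 on days 14-20: no reminder.
- Injection 2 on days 21-28: reminder.

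Both ranges satisfy the minimum spacing of 14 days. The flow chart's column for injection 2 mentions 14-21 days; within that range only day 21 triggers the reminder for a visit on day 28. Since injection 2 is booked for everyone, its date is mainly a matter of scheduling. Response enters through cancellation, but both good and poor responders may cancel, so the net effect on the arms has no clear sign.

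**3. Size of any distortion**

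Let d be the average shift in a rating caused by the reminder, taken as equal in both arms, and p1 and p0 the prompted shares in the two arms. The distortion of the difference in mean radicular pain at a visit is

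d × (p1 - p0).

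It is zero when p1 = p0. The documents give neither d nor the shares. Assume d is 0.5 to 1.5 points in size, with unknown sign.

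*Later visits, injections evenly spread.* Assume injections after day 28 fall evenly up to day 365, which is 365 - 28 = 337 days. The trigger window has 8 days, counting both ends.

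- Chance that one injection falls in the window before a given visit: 8/337 = 2.4%.
- Extreme split, with three such injections for every patient in one arm and none in the other: 3 × 8/337 = 7.1 percentage points. The chances add because injections at least 14 days apart cannot both fall in one 8-day window.
- Distortion: 0.5 × 0.071 = 0.04 to 1.5 × 0.071 = 0.11 points.

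*Week 12, injections clustered.* Assume one injection for every patient in one arm only, all in the 84 - 28 = 56 days before the week-12 visit.

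- Share difference: 8/56 = 14.3 percentage points.
- Distortion: 0.5 × 0.143 = 0.07 to 1.5 × 0.143 = 0.21 points.

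*Week 4.* The share difference cannot be bounded from the documents, because the dates on which injection 2 will be given are unknown. Each 10 percentage points of difference would contribute 0.5 × 0.10 = 0.05 to 1.5 × 0.10 = 0.15 points.

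**4. A related inconsistency**

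A flow-chart footnote lists calls after injections 1, 3 and 4 only. The visit text treats injection 2 as also having call data. If the footnote governs, injection 2 leaves no call data to collect at week 4, and most of the exposure at that visit disappears. If the visit text governs, it stays.

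**The case against.** The strongest reply is that the text shows an unclear instruction, not a prompted outcome. Several parts of that reply stand.

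- A reader might infer that patients at all other visits definitely rate pain without hearing the baseline. The protocol is silent on this and does not forbid a reminder. The data collection forms, which could show wording and order, are not in the copy available.
- A reader might infer that the prompted answer is the visit's outcome score. The visit text can be read as adding call data to the visit's own score. The flow-chart footnote reads more like a single recording. The documents do not decide between them.
- A reader might infer that week 4 shows prompting driven by response. It does not: injection 2 is booked for everyone in both arms, and its date is mainly logistical.
- The Statistical analysis section does not spell out a between-arm test of pain. It names associations of surgery avoidance with pain and other variables, so the comparison at risk is one the secondary outcome implies.

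What the reply does not remove is that a reminder is scripted for some scheduled visits and not for others, that no separate unprompted score is required, and that eligibility for the reminder depends partly on response through injections 3 and 4 and the cancellation of injection 2.

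**Conclusion.** The point holds as a measurement inconsistency in one component of a secondary outcome. Followed as written, the plan can mix prompted and unprompted radicular pain scores, according to injection timing.

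It would be tempting to conclude that the pain result is biased, or biased toward one arm. The documents do not support that: they give neither the effect of the reminder nor the prompted shares, and equal shares mean no bias. At later visits any distortion is probably small. The 0.04 to 0.21 points above rest on an assumed shift of 0.5 to 1.5 points, an all-or-none split between arms, and the stated spread of injection dates. Injections concentrated just before visits would raise it. Neck pain and the primary outcome are not affected. The change is worth making because it is cheap.

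**What to change.** In Follow-up Office Visits and on the visit form, state that current neck and radicular pain are recorded first at every office visit, without mention of the baseline score. Where call data are due, give the reminder afterwards and store the second radicular rating in a separate field as call data. State in Statistical analysis that only the unprompted visit score is used for the secondary pain outcome.

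Reconcile the flow-chart footnote on which injections are followed by a call with the visit text, so that it is clear whether injection 2 generates call data.

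The cost is a changed question order, a few sentences of text, and one extra rating at affected visits. Treatment and visit schedule are unchanged.
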